View Drug Purchase Tasks (DPT)	P3-FLUX-Drug Purchase Tasks_04.26.2021_CLEAN.docx	0.03	4/26/2021 12:23 PM	[name]	Research Measure	Yes
View Puff Limiting Software Details	P3-Flux Puff Limiting Software.docx	0.01	3/19/2021 3:54 PM	[name]	Other	Not Applicable
View Consent - Tool VIDEO	No_Longer_Using_This_Tool.docx	0.03	1/26/2021 11:37 AM	[name]	Other	No
View Facebook Advertisements	facebook ads_01.25.2021.docx	0.01	1/26/2021 10:16 AM	[name]	Recruitment/Advertising	Yes
View Combined PRT/CP-PRT - Tool	1.19_21_combinedPRT_instructions.pptx	0.02	1/25/2021 9:20 PM	[name]	Other	Yes
View Progressive Ratio Task (PRT)	PRT_FLUX_V3_1.22.21.pdf	0.03	1/25/2021 9:19 PM	[name]	Research Measure	Yes
View Subjective Measures	P3-FLUX-Session Subjective Measures_01.25.2021_CLEAN.doc	0.05	1/25/2021 4:45 PM	[name]	Research Measure	Yes
View CP-PRT - Tool	No_Longer_Using_This_Tool.docx	0.02	9/30/2020 1:48 PM	[name]	Other	No
View PRT - Tool	No_Longer_Using_This_Tool.docx	0.02	9/30/2020 1:47 PM	[name]	Other	No
View Subjective Measures - Tool VIDEO	Subjective Measures presentation_09.02.2020.mp4	0.01	9/9/2020 10:54 PM	[name]	Other	Yes
View Subjective Measures -Tool	Subjective Measures presentation_09.02.2020.pptx	0.02	9/9/2020 10:38 PM	[name]	Other	Yes
View Cross Product Progressive Ratio Task (CP-PRT)	CP_PRT_Flux_V2_08.04.2020.pdf	0.02	8/17/2020 11:46 AM	[name]	Research Measure	Yes
View Flux Advertisements	FLUX_Combined Ads_07.20.2020_V3_CLEAN.pdf	0.05	7/20/2020 10:32 AM	[name]	Recruitment/Advertising	Yes

Document Name	Document	Version	Date Modified	Uploaded By	Type	Approved
View CSTP Registry Consent Document	CSTP_Consent and screening_registry questions updated 4.29.19 CHANGES ACCEPTED.pdf	0.01	4/2/2020 3:36 PM	[name]	Consent/Assent/Information Sheet	Not Applicable
View BHRL Registry Consent Document	HM20007677 Consent Form_06.21.2019_CLEAN.pdf	0.01	4/2/2020 3:33 PM	[name]	Consent/Assent/Information Sheet	Not Applicable
View Presession Symptom Questions	P3-FLUX-Presession symptom Checklist-01.09.2019.docx	0.01	4/2/2020 12:47 AM	[name]	Research Measure	Yes
View [name] Biosketch	P3 [name] biosketch 06.22.17.FINAL.docx	0.01	4/1/2020 11:23 PM	[name]	CV/Biosketch	Not Applicable
View [name] Biosketch	[name] Biosketch_10.5.16.docx	0.01	4/1/2020 11:22 PM	[name]	CV/Biosketch	Yes

Finally, participants who are eligible following the in-person screening will be given 5 cards with information about our laboratory and a numerical/alphabetical code that is linked to that participant (name, e-mail address). These cards could be given to friends/family members who might want to participate in any of the lab's studies which include an in-person screening visit. If a friend/family member with a card appears eligible to participate (via the CSTP registry), comes to an in-person screening visit, and brings the card (for any of our studies that include an in-person screening visit) we will send the original participant \$20 per card via Amazon gift code to their e-mail address. The original participant will not be told who brought in the card(s). In total, the maximum a participant could receive from this referral program is \$100. Because of the relatively low amount of money participants can earn from this referral program, as well as the low likelihood all 5 cards linked to one participant will be brought back to the laboratory, we do not feel this strategy is coercive.

2. All payments will be in the form of cash with the exception of the follow-up survey and the referral card payments (Amazon gift card via email).

3. Payments are dispersed by the research staff in-person or via email.

4. Payment amounts were derived from previously performed studies at this lab and other groups with similar activities/participant populations.

2. If compensation will be pro-rated, explain the payment schedule.

Eligible & ineligible participants will be paid \$15 for their responses/in cash at the completion of the in-person screening.

Eligible participants will have an opportunity to complete a behavioral measure (BART) at the in-person screening. They can earn up to \$40.

If enrolled, compensation will be \$75 session 1, \$100 for session 2, \$100 for session 3, \$100 for session 4, and \$125 for session 5.

Participants will receive \$10 for the follow-up survey.

This makes for total potential compensation of \$55 from the in-person screening and \$510 from session/follow-up procedures (up to \$565 in total across the entire study).

If a session must be discontinued for reasons beyond the control of the participant, the participant will be paid for the time spent complying with study conditions before the session began (\$15) and also the time spent in the laboratory (\$15/hour).

Regarding the referral fee program - Participants receive \$20 per card returned via Amazon gift code to their e-mail address. In total, the maximum a participant could receive from this referral program is \$100.

Contingency Plan

This page will be used by the IRB in the event that an institution-wide emergency situation arises that requires contingency plans.

A contingency plan describes the alternative procedures that a study would want to use in case of an emergency that prevented normal study activities from occurring. It is a form of adaptive protocol. It enables the VCU IRB to quickly approve alternative study activities along with criteria for when those activities would or would not be put into effect. For example, in 2020, some studies had a COVID-19 Contingency Protocol approved that described alternative remote procedures that they would switch to whenever the University restricted in-person research activities.

In all studies, investigators are strongly encouraged to plan prospectively and build flexibilities into their regular protocols (regardless of whether an emergency situation exists) as well as think about what they would do in an emergency situation. For example, windows for timed study visits, ranges instead of exact values, flexibilities in inclusion criteria, etc. Flexibility and adaptations that are built into the protocol will reduce the number of changes that have to be submitted to the IRB and should reduce the number of incidents of deviations and noncompliance by investigators.

Further instructions and smartform questions on this page will be released from the IRB in the event of such an institution-wide emergency situation.

Research Complete

Progress:

1. PROTOCOL SETUP**2. BACKGROUND, RATIONALE & GOALS****3. RESEARCH PLAN**

- ④ CONSENT PLAN
- ⑤ RISKS, PRIVACY & CONFIDENTIALITY
- ⑥ POPULATIONS WITH SPECIAL CONSIDERATIONS
- ⑦ INSTITUTIONAL REQUIREMENTS
- ⑧ DOCUMENTS

Click Continue below to go to the next section

Consent Process

1. * List all consent groups:

View	Group Types	Waivers	Roles	Roles	Electronic Signatures	Consent	Coercion	Decision	Re- Consent
				- Other					
	In-person consent	Signed Consent by Participant	No Waivers Requested	Principal Investigator Co/Sub-Investigator Research Coordinator Research Assistant Trainee/Student(working on project)	Not using electronic signature platforms	Consent will be obtained in a private room located at the Center for the Study of Tobacco Products (CSTP). Consent will be obtained at in-person screening. Consent will be ongoing and assumed when a participant makes and completes follow up appointments. Participants are read the consent form aloud via a pre-recorded voice-over Powerpoint presentation/video or in real-time by a staff member and encouraged to ask questions before signing. At any point participants can chose not to continue with the various levels of screening for this study (the online/telephone consent/screening and in-person consent/screening).	Removing physical symbols of authority like white coats or police badges Sitting down research beside the participant instead of standing over them Other protection(s) not listed here – describe below		Participants will be given as much time as necessary to consider the study and consent form before deciding whether or not to participate.

2. Upload any consent / assent documents:

Document Name	Document	Version	Date Modified	Uploaded By	Type	Approved
View Informed Consent	P3 FLUX_Informed Consent_12.07.2022_CLEAN.pdf	0.29	2/27/2023 12:23 AM	[name]	Consent/Assent/Information Sheet	Yes
View Consent - Tool	P3FLUX_Consent_Presentation_12.07.2022_CLEAN.pptx	0.13	12/7/2022 2:37 PM	[name]	Other	Yes
View Text, Email, Call Scripts	Phone_e-mail_text scripts_CLEAN_12.07.2022.docx	0.19	12/7/2022 2:35 PM	[name]	Other	Yes
View COVID-19 Questions	NO LONGER USING_COVID_Questions_P3_12.07.2022.docx	0.06	12/7/2022 2:33 PM	[name]	Other	No
View Information about Blood Pressure	BP results P3 flux 8.22.2022.docx	0.01	8/22/2022 11:43 AM	[name]	Other	Yes
View P3 Flux Advertisement for CSTP Website	P3 FLUX Description for CSTP Website_CLEAN_03.30.2022.docx	0.05	4/13/2022 10:36 AM	[name]	Recruitment/Advertising	Yes

Document Name	Document	Version	Date Modified	Uploaded By	Type	Approved
View Referral Program Card Template	P3_Referral program card_1.13.2022.docx	0.01	1/14/2022 11:49 AM	[name]	Recruitment/Advertising	Yes
View Baseline Self Report Physio Measures	P3- FLUX_Baseline forms All_5.21.2021_CLEAN.docx	0.14	5/24/2021 2:01 PM	[name]	Research Measure	Yes
View Follow-up Survey	P3-FLUX-Follow-up_05.21.2021_CLEAN.docx	0.11	5/24/2021 1:59 PM	[name]	Research Measure	Yes
View CP-DPT & DPT - Tool	DPT_CDPT presentation_04.26.2021_CC.pptx	0.03	4/26/2021 4:36 PM	[name]	Other	Yes
View DPT/CP-DPT - DPT_CDPT presentation_04.26.2021_CC.mp4 Tool VIDEO		0.02	4/26/2021 4:35 PM	[name]	Other	Yes
View Drug Purchase Tasks (DPT)	P3-FLUX-Drug Purchase Tasks_04.26.2021_CLEAN.docx	0.03	4/26/2021 12:23 PM	[name]	Research Measure	Yes
View Puff Limiting Software Details	P3-Flux Puff Limiting Software.docx	0.01	3/19/2021 3:54 PM	[name]	Other	Not Applicable
View Consent - Tool VIDEO	No_Longer_Using_This_Tool.docx	0.03	1/26/2021 11:37 AM	[name]	Other	No
View Facebook Advertisements	facebook ads_01.25.2021.docx	0.01	1/26/2021 10:16 AM	[name]	Recruitment/Advertising	Yes
View Combined PRT/CP-PRT - Tool	1.19_21_combinedPRT_instructions.pptx	0.02	1/25/2021 9:20 PM	[name]	Other	Yes
View Progressive Ratio Task (PRT)	PRT_FLUX_V3_1.22.21.pdf	0.03	1/25/2021 9:19 PM	[name]	Research Measure	Yes
View Subjective Measures	P3-FLUX-Session Subjective Measures_01.25.2021_CLEAN.doc	0.05	1/25/2021 4:45 PM	[name]	Research Measure	Yes
View CP-PRT - Tool	No_Longer_Using_This_Tool.docx	0.02	9/30/2020 1:48 PM	[name]	Other	No
View PRT - Tool	No_Longer_Using_This_Tool.docx	0.02	9/30/2020 1:47 PM	[name]	Other	No
View Subjective Measures - Tool VIDEO	Subjective Measures presentation_09.02.2020.mp4	0.01	9/9/2020 10:54 PM	[name]	Other	Yes
View Subjective Measures - Tool	Subjective Measures presentation_09.02.2020.pptx	0.02	9/9/2020 10:38 PM	[name]	Other	Yes
View Cross Product Progressive Ratio Task (CP-PRT)	CP_PRT_Flux_V2_08.04.2020.pdf	0.02	8/17/2020 11:46 AM	[name]	Research Measure	Yes

1. PROTOCOL SETUP

2. BACKGROUND, RATIONALE & GOALS

3. RESEARCH PLAN

4. CONSENT PLAN

- ⑤ RISKS, PRIVACY & CONFIDENTIALITY
- ⑥ POPULATIONS WITH SPECIAL CONSIDERATIONS
- ⑦ INSTITUTIONAL REQUIREMENTS
- ⑧ DOCUMENTS

Click Continue below to go to the next section

Risks, Discomforts, Potential Harms and Monitoring

1. * Describe the risks of each research procedure to participants or others. For each identified risk, provide an assessment of the anticipated seriousness and likelihood of the risk. Some examples of possible risks include but are not limited to:

- Physical risks (e.g. bodily harms or discomforts, side effects, etc.)
- Psychological risks (e.g. emotional, mental, or spiritual harms or discomforts, changes to thoughts, beliefs, or behaviors, etc.)
- Research data risks (e.g. loss of confidentiality and privacy)
- Social or legal risks (e.g. impacts on relationships or reputation, legal or criminal justice actions for self or others, etc.)
- Financial risks (e.g. impacts on income, employability, or insurability, loss of services, etc.)
- Other risks (e.g. unforeseeable risks of experimental procedures, risks related to particular study designs (randomization, washout, placebo, withholding care/services, deception), etc.)

See the help text for additional guidance.

There are few risks associated with this study.

1. Participants may experience some mild discomfort during the 12-hour tobacco/nicotine abstinence period before each session. Side effects from tobacco/nicotine abstinence can include irritability, anxiety, restlessness, excessive hunger, difficulty concentrating, and sleep disturbance. Though uncomfortable, these feelings are not medically dangerous.

2. There is some risk of frustration while completing study procedures.

3. We have read that users of the ECIG device we are using in this study sometimes experience small drops of liquid during inhalation, and we have occasionally noticed this during our testing of the product. If this occurs, participants may find the droplets unexpected and/or unpleasant. We believe that is unlikely that these small droplets of liquid present any medical danger.

4. The ECIG liquid used may contain more nicotine than participants normally ingest, but these effects are unlikely in individuals who use cigarettes regularly. Participants also might experience side effects from products that contain nicotine such as acute increases in heart rate and blood pressure, sweating, lightheadedness, dizziness, nausea, and nervousness.

5. The Centers for Disease Control and Prevention advises that e-cigarette, or vaping products are unsafe for youths, young adults, or women who are pregnant. Adults who do not currently use tobacco products should not start using e-cigarette, or vaping, products. If you use e-cigarette products, monitor yourself for all of these symptoms and promptly seek medical attention if you have concerns about your health.

a. Some people who use e-cigarettes have reported experiencing seizures. Some of these individuals reported a prior history of seizures or using other substances at the same time as their e-cigarette.

b. In some cases, e-cigarette use has led to respiratory illnesses such as difficulties breathing, shortness of breath, cough, and/or chest pain before hospitalization. In some cases, e-cigarette use has led to death, although most of these cases have been related to vaping THC.

c. In some cases, symptoms of mild to moderate gastrointestinal illness such as nausea, abdominal pain, vomiting, diarrhea, or fevers or fatigue have been reported.

6. The use of e-cigarettes may include other side effects/risks such as a sore or scratchy throat and headache.

7. There is some risk of illness/contamination due to ECIGs being reused between participants.

8. There is some risk of loss of confidentiality.

There is little available data on the range of power settings (in Watts) and liquid concentrations that ECIG users use. One paper described data on power and liquid settings for 165 adult users in California, which showed a median power setting of 204.5 W, although the authors note that many participants were not able to accurately report their power settings. In the same study, the median liquid concentration was 6.0 mg/ml nicotine with a range of 0 - 30.0 mg/ml. Data collected in an ongoing study in the CSTP for N = 44 shows an average power setting of 55.3 W (range = 6.8 - 204 W) and a mean liquid concentration of 7.6 mg/ml nicotine (range = 3 - 18 mg/ml). We have conducted a variety of ECIG studies previously in the CSTP with liquid that is 36 mg/ml nicotine. Finally, information from e-cigarette forums indicates that individuals are using both low and high nicotine liquids (35 - 50 mg/ml, for example) in "third generation", variable-wattage devices like the one we are proposing to use in this study.

2. * Describe how each of the risks/harms/discomforts identified above will be minimized:

Tobacco/nicotine abstinence syndrome: As individuals entering this study may exhibit signs of nicotine dependence there is a possibility that during the 12-hour tobacco/nicotine abstinence period prior to each session, participants may

experience symptoms associated with tobacco/nicotine abstinence including irritability, anxiety, restlessness, hunger, and difficulty sleeping. Importantly these effects can be uncomfortable but are not medically dangerous. Participants will be informed of these potential abstinence-related side effects during the informed consent.

During the sessions, if the participant reports experiencing small droplets of ECIG liquid during inhalation, we will immediately replace the device he or she is using in the session.

We will inform participants of the other ECIG-related side effects during the informed consent process. These risks are minimized by limited exposure to ECIGs in study sessions. We do not anticipate participants taking more than 40 puffs per session.

The risk of seizures is minimized by excluding participants with any history of seizures, and by having a full-time RN available, as well as monitoring of vital signs. In addition, some of the reported seizures occurred in users who were using other substances such as marijuana or amphetamines--the risk of seizures in this study is reduced as we are administering nicotine and no other substances.

The risk of respiratory illnesses related to ECIG use is minimized by the limited ECIG use that occurs in each session. Participants are expected to take no more than 40 puffs of either their own brand CIG or the session-specific ECIG at each session. Participants are informed about recent reports of ECIG-related respiratory illnesses and are informed that the CDC has advised people to stop vaping. Participants are also advised to monitor themselves for symptoms and to seek medical attention if they have concerns. In addition, we will ask about respiratory and gastrointestinal symptoms at screening and before each session begins. Answers given at the beginning of each session will be compared to the participants' previous answers, and if any symptoms have increased, [name] will be asked to review the symptoms. In some cases, we may contact [name] to determine if a session can proceed.

We recruit individuals aged 18+ who use nicotine-containing products at similar or higher daily/weekly frequencies that they would be exposed in the laboratory setting. For example, our cigarette smokers must report smoking at least 5 cigarettes per day or at least 1 cigarette/day and at least weekly use of another inhaled tobacco product and a positive cotinine cassette test to verify nicotine use. Their laboratory-based product exposure will be limited to the 4 test puffs at the beginning of the session and puffs that they may take as part of the PRT (no puff limit provided; self-directed by the participant) and CP-PRT (limited to a maximum of 10 puffs; self-directed by the participant). We do not expect participants to take more than 40 puffs across the entire session/tasks (~3.5 hours) based on our experience with these tasks and ECIG conditions used previously. Considering only a minimum of 4 tobacco product puffs are required (other puffs are self-directed and/or restricted in number) our protocol ensures that study-related nicotine/tobacco exposure is similar to or less than what participants may expose themselves to as part of their ordinary life.

Nicotine-related side effects: It is possible that participants may experience unpleasant symptoms associated with over consumption of nicotine during study sessions when tobacco products are administered (e.g., increased heart rate/blood pressure, dizziness, nausea). Importantly, this population will have experience with nicotine consumption. We will exclude individuals at baseline screening that have high blood pressure (meet safety criteria defined below) or withdraw those enrolled if we observe repeated high blood pressure during study sessions (dependent on consultation with medical monitor). The likelihood of these effects is very low. As part of the informed consent process, we will inform participants of potential side effects associated with nicotine consumption.

Our sessions and surveys are optimized in length to make them as short as possible while ensuring collection of primary study outcomes. We believe a 4-hour session and the number of subjective and behavioral assessments per session are not worthy of noting as discomforting.

Though ECIGs will be reused every participant will receive a new disposable mouthpiece that is placed on the ECIG mouthend of the device at each session. Additionally the ECIGs will be cleaned between sessions with rubbing alcohol and water.

Loss of confidentiality is a possibility but we minimize this risk by using a double locked filing cabinet, a password protected database (REDCap) and limiting access to authorized study personnel only. We also assign a unique ID code to participants instead of using their name or other identifiable data to track their participation.

The support of the research staff will minimize potential frustration during study sessions. Research staff will be available for questions and support throughout the study sessions. If ever study tasks become unmanageable, participants will be offered the opportunity to end the session early and potentially repeat the session at a later date or to discontinue participation. The study staff is well trained to identify signs of frustration and proper support responses.

3. * Describe any potential risks or harms to a community or a specific population based on study findings (e.g. information that could be stigmatizing or derogatory):

None

4. Where appropriate, discuss provisions for ensuring necessary medical, professional, or psychological intervention in the event of adverse events to the subjects:

Individuals whose BP levels are elevated (≥ 140 mmHg systolic or ≥ 90 mmHg diastolic) during baseline screening or at a session will be provided with a blood pressure information sheet by the research staff (see study document). This sheet will be provided at the first instance of elevated blood pressure observed during the study.

Research personnel are trained to alert the research nurse if heart rate continually exceeds 120 beats per minute, if systolic BP continually exceeds 160 mm Hg, or if diastolic BP continually exceeds 100 mm Hg. Individuals whose heart rate and/or BP levels remain elevated will be monitored by the research nurse and if, necessary, emergency responders will be notified. Emergency medical coverage will be available via the emergency room that is 1.5 miles from the CSCP.

5. * Describe criteria for when the investigator would withdraw an individual participant from the study; such as safety or toxicity concerns, emotional distress, inability to comply with the protocol, etc.:

Participants may be withdrawn from the study if the PI or study nurse has any safety concerns (such as high blood pressure or heart rate) during sessions.

The PI/research nurse and/or Medical Monitor will be consulted/notified via phone/email specifically concerning high

blood pressure observations that occur during any study session to determine whether a participant should remain in the study.

If a participant does not comply with the 12-hour tobacco/nicotine abstinence requirement (which can be difficult for some participants), we allow participants to re-schedule a session. We allow multiple attempts, but do not have a specified number of attempts that are allowed, as it depends on the circumstances of each participant.

6. * Summarize any pre-specified criteria that would trigger the investigator/sponsor/monitoring committee to stop or change the study protocol due to safety concerns:

We do not have any prespecified criteria for stopping or changing the study protocol due to safety concerns.

Data and Safety Monitoring

Data and safety monitoring is a system for checking the study's data at regular intervals over the study period to identify and address issues that could affect the safety of research participants. This requirement is in accordance with 45 CFR 46.111.

The purpose of data and safety monitoring plan is to set forth study team procedures for monitoring/addressing:

- Participant safety (physical, psychological, etc.)
- Data validity
- Early stopping (termination) based upon changes in risks and benefits.

7. * Indicate if this study will have a Data Safety Monitoring Board (DSMB) or a Data Safety Monitoring Plan (DSMP): [Required for all greater than minimal risk studies]

DSMB
 DSMP
 No DSMB/DSMP [Note: This response is not applicable for greater than minimal risk studies]

8. * Describe your Data Safety Monitoring Plan for monitoring the study's data to ensure the safety of participants. This plan should include (but is not limited to) the following elements:

1. Who will monitor data
2. What data and/or processes will be reviewed
3. When and how frequently monitoring will occur
4. What report/documentation will be submitted to the IRB at the time of continuing reviews

See the help text for additional guidance.

1. Who will monitor data: The Co-PIs (Drs. [name] and [name]) and the medical monitor ([name])

2. What data and/or processes will be reviewed:

- Baseline sociodemographic characteristics of enrolled study participants
- Reasons for ineligibility following in-person screening
- Retention and disposition of study participants including any complaints about the study and reasons for participant withdrawal
- Responses to the pre-session symptom checklist
- Protocol deviations/violations
- Any other regulatory issues
- Adverse events
- Serious adverse events
- Unanticipated problems

3. When and how frequently monitoring will occur:

Any adverse events and protocol deviations/violations that occur during the study sessions will be monitored and documented by the research staff and communicated as soon as possible to PI/medical monitor for review/response. We will follow VCU IRB reporting requirements for all adverse events and protocol deviations/violations that may occur. We also will review all of the items listed in #2 in a summary report annually.

4. What report/documentation will be submitted to the IRB at the time of continuing reviews:

A summary report that includes all of the items listed in #2 will be submitted to the IRB at the time of the continuing reviews.

Privacy

Privacy refers to an individual's right to control how others view, record, or obtain information about them. When privacy is violated it can involve such things as

- Being asked personal questions in a public setting;
- Being publicly identified as having a particular characteristic or diagnosis;
- Being seen entering a place that might be stigmatizing;
- Being photographed, videotaped or observed without consent;
- Disclosure of personal information to unauthorized people

Privacy is not the same as confidentiality because privacy protections apply to people, and confidentiality protections apply to data. Confidentiality protections should be described on the Data Confidentiality page of this form, not here.

Instructions for this page:

Select all the applicable ways that the research team will protect participants' privacy throughout the course of the study. The options listed include some of the most common best practices. Not all will be applicable to every study.

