This study manipulates e-cigarette nicotine flux systematically, testing the hypothesis that abuse liability will be related directly to flux among a sample of cigarette smokers. No previous study has manipulated nicotine flux and examined within-group effects, so we could not estimate effect size. Thus, we calculated a sample size to achieve a power of >0.80 with $\alpha <0.05$ and assuming a small effect size (Cohen's $f=0.20$) and moderate repeated measures correlation ($r=0.5$) in a repeated measures ANOVA with nicotine flux as within-subjects factors (N=32; GPower). In Study 2, 40 cigarette users will attend the lab for 5 sessions - no flux, low flux, cigarette-like flux, high flux, and an own brand cigarette control (always session 5). We hypothesize that flux will be positively associated with willingness to pay/work (drug purchase task, progressive ratio task) and willingness to substitute e-cigarettes for own brand cigarettes (cross-product drug purchase task, cross-product progressive ratio task), and inversely to price sensitivity (drug purchase task) for all smokers.

It is possible that we would consent up to 100 participants in order to obtain 40 participants who complete the entire study.

4. * List the study inclusion criteria:

All participants must be healthy (determined by self-report), between the ages of 18-55 (verified by photo ID), willing to provide informed consent, and attend the lab and abstain from tobacco/nicotine as required. Participants must agree to use designated products according to the study protocol.

Participants must use at least 5 cigarettes per day if they are not classified as dual users of inhaled tobacco products.

Participants classified as dual users of inhaled tobacco products must meet at least of two definitions described below:

- at least some day use of cigarettes (≥ 3 days per week at any cigarettes per day frequency) AND
- daily use of another inhaled tobacco product (e.g., e-cigarettes, cigars, pipe)

OR

- daily use of cigarettes (at any cigarettes per day frequency) AND
- at least some day use of another inhaled tobacco product (e.g., e-cigarettes, cigars, pipe; ≥ 3 days per week at any frequency).

Participants must have a 'positive' cotinine cassette result to verify nicotine use.

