Please note that beginning July 1, 2020, per HB1570, we will recruit individuals aged 18-55. This law "Provides an exception to the law prohibiting possession of tobacco products, nicotine vapor products, or alternative nicotine products by a person less than 21 years of age when such possession is part of a scientific study being conducted by an organization for the purpose of medical research to further efforts in cigarette and tobacco use prevention and cessation and tobacco product regulation, provided that such medical research has been approved by an institutional review board pursuant to applicable federal regulations or by a research review committee." We will not enroll any participants under the age of 21 until after July 1, 2020.

5. * List the study exclusion criteria:

Individuals with the following self-reported current, diagnosed medical condition(s) will be excluded automatically: uncontrolled high blood pressure (i.e., self-reported and/or observed at screening; BP above 160/100), recent heart attack/stroke, coronary heart disease, severe immune system disorders (e.g., HIV/AIDS, multiple sclerosis), respiratory disorders (e.g., COPD, asthma), kidney diseases, liver diseases (e.g., cirrhosis), or seizures.

Individuals with other self-reported current, diagnosed medical conditions (e.g., diabetes, thyroid disease, lyme disease) will be considered for exclusion after consultation with the PI and medical monitor. Participants with any medical condition/medication that may affect participant safety, study outcomes, or biomarker data will be excluded based on these consultations.

Participants with self-reported current, diagnosed psychiatric conditions, and who are currently under the care of a physician for psychiatric conditions, or who report current psychiatric treatment or psychotropic medication use will be excluded.

Individuals with past-month use of other illicit drugs including cocaine, opioids, benzodiazepines, and methamphetamine will be excluded.

Individuals who report using marijuana ≥ 16 days in the past 30 and/or alcohol ≥ 26 days in the past 30 days will be excluded.

Those who intend to quit tobacco/nicotine use in the next 30 days will be excluded and referred to cessation treatment.

Use of other tobacco products (other than cigarettes) at any frequency will NOT be exclusionary.

Women will be excluded if they are breast-feeding or test positive for pregnancy (by urinalysis) at the screening.

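### The risk section promises exclusion of any seizure history, but the exclusion list covers seizures only as a current, diagnosed condition

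*Combined protocol and SAP*

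**What the plan says.** The application states the seizure exclusion in two places.

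- **Risks, Discomforts, Potential Harms and Monitoring, item 2** (how risks are minimised): "The risk of seizures is minimized by excluding participants with any history of seizures". The same sentence adds two further measures: "and by having a full-time RN available, as well as monitoring of vital signs".
- **Study Population, item 5** (exclusion criteria). The automatic list opens: "Individuals with the following self-reported current, diagnosed medical condition(s) will be excluded automatically". It ends: "respiratory disorders (e.g., COPD, asthma), kidney diseases, liver diseases (e.g., cirrhosis), or seizures". The seizure entry has no time qualifier.

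Item 5 then provides a second tier, which the PI settles case by case together with the medical monitor: "Individuals with other self-reported current, diagnosed medical conditions (e.g., diabetes, thyroid disease, lyme disease) will be considered for exclusion". The next sentence reads: "Participants with any medical condition/medication that may affect participant safety, study outcomes, or biomarker data will be excluded based on these consultations". The inclusion criteria (item 4) require participants to be healthy by self-report and do not mention seizures.

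**The concern.** The two statements differ in scope. The risk section covers a lifetime history. The criteria list, on its face, covers a current diagnosed condition. A person who had a seizure some years ago and carries no present diagnosis falls between them.

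The application itself explains why this group matters. Both the Risks section (item 1) and Behavioral Intervention/Task Details (item 2) say that some e-cigarette users who reported seizures had had seizures before. Of the measures in the risk-minimisation sentence, exclusion is the only one that keeps such a person from being exposed. The nurse and the vital-sign monitoring act once a session is under way, and the stated nurse-alert triggers (item 4 of the same section) are heart rate and blood pressure.

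Secondary Data/Specimen Details, item 1, says that all eligibility criteria are evaluated again at the in-person screening. The wording of the criteria is therefore what should deliver the safeguard described to the IRB.

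**Working it through.** The plan gives no figure to reproduce. The check is to apply each written rule to one test case: a past seizure, no current diagnosis, otherwise eligible.

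| Rule | Scope as written | Automatic exclusion of the test case? |
|---|---|---|
| Risks section, item 2 | Any history of seizures | Yes, but this text is not in the criteria list |
| Study Population, item 5, automatic list | Self-reported, current, diagnosed conditions, including seizures | No, read literally |
| Item 5, consultation clause, first sentence | Other current, diagnosed conditions | No; not current, and only considered for exclusion |
| Item 5, consultation clause, second sentence | Any condition that may affect safety | No; depends on the outcome of a consultation |
| Item 4, healthy by self-report | General; seizures not named | No; a person years past a seizure may honestly report being healthy |

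Only the risk section excludes the test case categorically.

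**Exposure if such a person were enrolled.** Inputs from Study Procedures, item 6: 4 sample puffs per session; four e-cigarette sessions, at 0, 6, 15 and 30 mg/ml.

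- One e-cigarette session attended: 4 sample puffs.
- All four completed: 4 × 4 = 16 sample puffs.
- Of these, from nicotine liquids (6, 15 and 30 mg/ml): 3 × 4 = 12.

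Task puffs are extra and self-directed. The progressive ratio task has no puff limit and the cross-product version allows at most 10. The plan expects no more than 40 puffs per session in total. Consent precedes screening and non-completers are replaced, so the 16 and 12 apply only to someone who completes all four e-cigarette sessions. These counts describe ordinary protocol exposure; they do not measure how many people the wording affects.

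**Room for extra screen failures.** Up to 100 consents are allowed to obtain 40 completers (Study Population, item 3): 100 − 40 = 60.

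**The case against.** The strongest reply is that the intended scope is already on record. The risk section is part of the same application and states it without qualification. The word *current* is also applied loosely in the exclusion list, which includes "recent heart attack/stroke, coronary heart disease, severe immune system disorders"; a recent heart attack is a past event. On that view, seizures are listed as events with no time limit, and the natural reading agrees with the risk section. A disclosed past seizure could also reach the PI and medical monitor through the consultation clause. The baseline form and the registry screener are listed but not reproduced, and may already ask about lifetime history.

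Much of this stands. The intent is clear, the stem is loose, and actual screening practice cannot be judged from the documents. None of it removes the conflict. Where the authors meant a past event they added a time word, as with heart attack and stroke, and they set explicit look-back windows for drug, marijuana and alcohol use. The seizure entry has none, so even a loose reading leaves open whether it means recent or ever. The consultation route is a judgement, while the risk section describes a categorical rule.

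The plan also says that study exposure is similar to or below participants' ordinary use. That leaves the added risk unquantified, but the plan still relies on the exclusion as a safeguard.

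**Conclusion.** The concern holds: the eligibility criteria, read as written, do not carry the seizure exclusion that the risk section relies on. The conclusion rests on the wording alone, and the difference in wording is certain.

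Three limits apply. The documents give no seizure prevalence, so the number of people affected cannot be estimated. The screening form is not shown, so nothing here establishes that anyone with a past seizure was or could be enrolled. No sample size, power, endpoint or analysis changes. The correction should still be made, because it aligns a participant-safety rule with what the IRB was told, at almost no cost.

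**What to change.** In Study Population, item 5, replace the seizure entry with: any history of seizures (lifetime, self-reported), as an automatic exclusion outside the current-and-diagnosed qualifier. Confirm that the screening question asks about lifetime history, and change that line of the form if it does not.

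The cost is one IRB text amendment, possibly a one-line form change, and perhaps a few more screen failures, for which the consent ceiling leaves room. The documents do not say whether enrolment is still open. If it has closed, the equivalent step is to confirm and record what the form asked, and to correct the written criterion.
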